Study Rationale	
Fructose consumption has dramatically increased over the past 20 years in the United States (US) and worldwide¹. High fructose intake has been shown to increase serum triglycerides, upregulate de novo lipogenesis, reduce fatty acid oxidation and decrease the clearance of very low density lipoprotein triglycerides in liver leading to nonalcoholic fatty liver disease (NAFLD)¹. Nonalcoholic fatty liver disease (NAFLD), the leading cause of chronic liver disease in the US, is characterized by fat accumulation in liver cells not caused by alcohol². A group of disorders including steatosis, nonalcoholic steatohepatitis with fibrosis and cirrhosis, NAFLD has substantially risen in prevalence over the last two decades with recent estimated prevalence being 20% among US adults and 25% in young adults (18-39 years).²
 
Although evidence has been presented for the positive relationship between fructose intake and NAFLD, the role of fructose in liver fat accumulation has been unclear. Individuals with specific genotypes seem to be more susceptible to the adverse metabolic effects of fructose. For example Hispanic children with rs738409 (GG) single nucleotide polymorphism (SNP) of patatin-like phospholipase, domain-containing 3 (PNPLA3) increased their liver fat by 23% more than CG/CC children exposed to the same amount of dietary fructose³. Similarly, adolescents with rs1260326 (TT) of glucokinase regulatory protein (GCKR) variant increased their de novo lipogenesis by 44% as compared to CC adolescents when given a sugar challenge⁴. Therefore, we hypothesize that when given the same amount of fructose individuals with specific set of genotypes will be more susceptible to increased de novo lipogenesis and liver fat accumulation than others.

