Study Objective(s)	
Our goal for this study is to generate preliminary data that is needed to support an application to NIH for funding of a larger, adequately-powered study to explore whether a set of genotypes, that increase the risk for nonalcoholic fatty liver disease (NAFLD), predispose individuals to increased de novo lipogenesis (DNL) and liver fat accumulation when exposed to fructose intake.
 
Primary Objective: To determine the impact of acute and prolonged exposure of fructose on hepatic lipid accumulation in adolescents and young adults (12-40 years) with high and low genetic risk for NAFLD using liver mass resonance imaging (MRI).
 
Secondary Objective: To explore the genetic-specific effects of fructose on markers of liver fat accumulation (fibroscan⁵ and fatty liver index⁶) and serum biomarkers related to lipids, uric acid and liver function.

Test Article(s) (If Applicable)	Sugar-Sweetened beverages
Study Design	
 a. We will screen 200 Caucasian children and young adults (12-40 years) to obtain 24 children and 24 young adults who are overweight/obese and drink <14 fructose drinks/week to participate in a 3-week fructose intervention study. The 200 participants will be genotyped for 10 SNPs involved in lipid metabolism and associated with increased NAFLD risk in previously published studies^{7,8}. We will select 12 children and young adults with 15 or more risk alleles and 12 children and 12 young adults with 6 or fewer risk alleles and provide them fructose + glucose⁹ drinks who will ingest one drink (equal to 2 soft drinks) per day for 3 weeks; b. We will measure liver fat using Liver MRI^{9,10} and transient elastography (Fibroscan)⁵ at week 0 and 3;

c. Data will be analyzed using paired and unpaired students T test to differentiate the responses between the time points and between the two groups, respectively.

Specific Aim2: Determine the impact of acute exposure of fructose on hepatic *de novo* lipogenesis

- Using the cohort described in Specific Aim1, we will conduct oral fructose tolerance test at week 0 and week 3;
- We will measure liver fat using Fibroscan
- Data will be analyzed using unpaired students T test and repeated measures ANOVA to differentiate the responses between and within the two groups, respectively.

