	(2) Intervention: This part is divided into two phases. Each phase entails two visits. Phase2-visit 1: The 48 enrolled (24 in each of the high and low genetic risk group) will

visit the UNC NRI clinical suite run by the Human Research Core. They will be taken to the WakeForest imaging center for their baseline MRS scan.

Visit 2: Acute fructose challenge: The next day, they will have their initial anthropometrics and Fibroscan measurements. They will then undergo an oral fructose challenge using a protocol used by Hudgins et al¹³. The participants will be provided with a drink consisting of fructose (0.75g/kg body weight) + glucose (0.45g/kg body weight) dissolved in 24 Oz of water (equal to 2 soda cans) to be consumed within 15 minutes. Blood and urine will be sampled at baseline and 1 and 3 hours after sugar drink ingestion. During the challenge period, no other beverage (except water) or food will be allowed.

3-week intervention: The 48 participants will be provided with sugar drinks for the three week period. The drinks that need to be taken per day will contain fructose (0.75g/kg body weight) + glucose (0.45g/kg body weight) dissolved in 24 Oz of water (equal to 2 soda cans) which is similar to that provided during the acute fructose challenge⁷.

[figure not shown]
Addition of glucose to fructose in the challenge and 3-week intervention induces the lipogenic effects of fructose, alleviates gastrointestinal effects of fructose and mimics the real-life situation¹⁴. They will visit at the end of each week to collect drinks for the next week. In addition, participants will be given standardized meals for the day prior to the baseline fructose challenge. They will also be instructed to avoid alcohol, juices and sodas the previous evening.

Efficacy Evaluations	Changes in liver fat accumulation through MRI scans and fibroscan measurements, and serum concentration of other lipids, liver function markers and uric acid.
Pharmacokinetic Evaluations	N/A

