We will conduct a spot glucose check using a glucometer (Accu-Chek, Roche Diagnostics, CH) to check that the glucose levels of the participants are in the normal range (fasting < 100mg/dl, post meal < 140 mg/dl and random < 200 mg/dl). The exclusion criteria includes ages < 12 and > 40 years, known alcohol abuse or fructose intake > 14 drinks per week, not of Caucasian ethnicity, glucose levels > 100 mg/dl if fasting, > 140mg/dl if within 2 hours post meal and > 200 mg/dl if random, and known diagnosis of diabetes, fructose intolerance and chronic kidney disease.

We will collect saliva from the eligible 200 children and young adults, extract DNA and genotype 10 SNPs shown in Table1.

Genotyping: SNPs will be genotyped from DNA extracted from saliva. Genotyping will be conducted in [name] lab using TaqManSNP genotyping assays (Applied Biosystems, Foster City, CA). The minor allele frequencies (MAFs) of these SNPs range between 7 and 49% based on Caucasian ethnic background. Therefore we are confident about finding 48 individuals with all 10 SNPs. If we don't find individuals with the 10 SNPs, we will mine the literature and find more SNPs that have a role in liver lipogenesis.

4.2

Intervention/Treatment procedures (by visits)

Phase2: Selection of 48 participants for the acute fructose challenge and 3-week intervention study:

The risk allele will be defined as the allele that is associated with higher levels of liver lipogenesis or fat as per previously published studies in Caucasians. The number of risk alleles will range from 0 to 20. The SNP will get a score of 2 with two risk alleles, 1 with one risk allele and 0 with no risk alleles. All the score will be added to get a cumulative score between 0 and 20 for 10 SNPs. We will select participants having > 15 risk alleles and < 6 risk alleles for our acute challenge and 3-week intervention study.

Phase 2&3- visit 1- MRI scan: The 48 individuals enrolled will visit the UNC NRI clinical suite run by the Human Research Core. After obtaining consent, they will be taken to the WakeForest Imaging center for baseline MRI scan. Studies have shown that 5-6% of liver fat is considered normal and anything more than that can reflect increased risk for fatty liver. If the MRI report of the participants shows liver fat > 6%, we will consult with the participant (if > 18years) and/or their parents in confidence and explain why they (or their child) cannot continue to

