6.3 Statistical Methods

Each subject will be given sugar drink containing fructose and liver MRI scan with fibroscan measurements will be taken at baseline and end of 3 weeks. Data will be assessed using descriptive measures and confidence intervals. Paired t-tests and repeated measures regression analysis will be performed to explore the significant differences between week 0 and week 3. Also, for each subject, the area under the curve (AUC)¹³ will be computed and a linear regression with AUC as the response will be performed during the acute challenge.

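### Name Welch's t test for the high- versus low-risk comparisons: Student's test is sound at the planned 24 v 24, but not if the achieved groups differ in both size and spread

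*Combined protocol and SAP*

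**What the plan says.** For Aim 1 the synopsis (Study Design, item c) specifies "paired and unpaired students T test to differentiate the responses between the time points and between the two groups". For Aim 2 it says "Data will be analyzed using unpaired students T test and repeated measures ANOVA", the t test being for the between-group part. Aim 3 again names Student's t test, with Pearson correlations. Section 6.3 adds "Paired t-tests and repeated measures regression analysis will be performed to explore the significant differences between week 0 and week 3". It names no between-group t test, no check of variances and no unequal-variance alternative.

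The planned groups are equal. The synopsis (Study Phases) gives 12 children and 12 young adults at each risk level, and describes the enrolled sample as "24 in each of the high and low genetic risk group". Section 4.1 expresses confidence in filling the groups: "Therefore we are confident about finding 48 individuals with all 10 SNPs". If suitable genotypes are not found, more SNPs are to be taken from the literature. The hypothesis in the Study Rationale is that "individuals with specific set of genotypes will be more susceptible to increased" lipogenesis and liver fat accumulation. No SD, alpha level or expected imbalance is given.

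**The concern.** Student's test estimates one common variance. With equal group sizes it tolerates unequal variances well. With unequal sizes it does not. If the smaller group is the more variable, the standard error is too small, so false positives are too frequent and intervals too narrow. If the larger group is the more variable, the opposite happens and power is lost.

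Equal groups are planned but not assured. Extreme risk scores are rare under the Table 1 frequencies. The baseline MRI takes place after genetic selection and removes participants with liver fat above 5% (one place in section 4.2 says 6%; the two need reconciling). Because section 4.2 defines risk alleles by their association with liver lipogenesis or fat, that exclusion may fall more heavily on the high-risk group, which is an inference. Section 4.7 allows withdrawal at any time. No replacement rule is stated.

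The comparison of risk groups is the study's genetic answer, and section 6.4 intends the data for sizing a larger study. A misstated interval would carry over into that planning.

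**Working it through.** **Inputs.** From the documents: 24 v 24, the Table 1 allele frequencies, and 200 screened. Assumed, because the documents give none: two-sided 5% level, normal data, SD ratios of 1 to 2, and unequal splits of 18 v 24 and 12 v 24.

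**The plan's own figure.** 4 cells × 12 = 48 = 24 + 24. It rests on no power calculation, so there is nothing further to reproduce.

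**Mechanism.** The true variance of the difference in means is V = s1²/n1 + s2²/n2. The pooled test estimates, on average, P = [((n1−1)s1² + (n2−1)s2²)/(n1+n2−2)] × (1/n1 + 1/n2). With SDs of 2 and 1:

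- 24 v 24: V = 4/24 + 1/24 = 0.208; P = (115/46) × 0.0833 = 0.208. Standard-error ratio √(P/V) = 1.00.
- 18 v 24, smaller group more variable: V = 4/18 + 1/24 = 0.264; P = (91/40) × 0.0972 = 0.221. Ratio 0.92.
- 12 v 24, smaller group more variable: V = 4/12 + 1/24 = 0.375; P = (67/34) × 0.125 = 0.246. Ratio 0.81.
- 12 v 24, larger group more variable: V = 1/12 + 4/24 = 0.250; P = (103/34) × 0.125 = 0.379. Ratio 1.23.

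**Rejection rate of Student's test when the means are equal**, by numerical integration over both sample variances and checked by simulation with 200,000 replicates:

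| Group sizes | More variable group | SD ratio 1 | SD ratio 1.5 | SD ratio 2 |
|---|---|---|---|---|
| 24 v 24 | either | 5.0% | 5.1% | 5.2% |
| 18 v 24 | smaller | 5.0% | 6.4% | 7.5% |
| 12 v 24 | smaller | 5.0% | 8.6% | 11.3% |
| 12 v 24 | larger | 5.0% | 2.7% | 1.8% |

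The nominal 95% interval covers at 100% minus these rates, whatever the true difference. At 12 v 24 that is 91.4% and 88.7% in one direction, and 97.3% and 98.2% in the other. Welch's test gives 4.9% at 24 v 24 (ratio 2) and 5.0% at 12 v 24 in both directions.

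**What Table 1 implies about group sizes.** Assume Hardy-Weinberg proportions and independent SNPs. If every minor allele were the risk allele, the mean score would be 2 × 2.88 = 5.76; about 132 of 200 would score 6 or fewer, and practically none 15 or more. The documents do not say which allele is the risk allele at each SNP, so all 2^10 = 1,024 assignments were tried. None gives 24 in both groups. The smaller group's expected count is at most about 3.0 with cut-offs of 15 or more and "6 or fewer risk alleles", and about 0.6 under section 4.2 ("We will select participants having > 15 risk alleles and < 6 risk alleles"). The high-risk group is the smaller in 620 assignments and the larger in 404.

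**Cost of Welch.** With equal variances and a true difference of 1 SD, there is no loss at 24 v 24. Power falls from 78.4% to 76.9% at 12 v 24 (1.5 points) and from 65.8% to 61.4% at 8 v 24 (4.4 points).

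**Limit of Welch.** Over SD ratios of 1 to 2 its own error rate is 6.9% to 7.6% at 3 v 24 and 11.6% to 12.4% at 2 v 24.

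**The case against.** The strongest reply is that the plan as written is sound: equal groups are specified, and at 24 v 24 Student's test holds its level. The study is also exploratory and concedes in section 6.4 that it may lack power, so a false-positive argument carries less weight. Both points stand, and they keep this at the level of an improvement.

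A reader might go further and infer a false-positive rate of about 9% to 18%, from a high-risk group that is both smaller and more variable. Those rates are arithmetically right for splits from 12 v 24 to 6 v 24 at SD ratios of 1.5 to 2 (18.5% at 6 v 24, ratio 2), but the documents do not support the premises:

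- The hypothesis concerns greater average susceptibility and says nothing about spread. If extra spread came only from a stronger response, it need not exist under the null, where Student's test stays at 5.0% for any split. The argument about interval coverage survives, because it does not depend on the null.
- Table 1 does not yield 6 to 12 v 24. Where the low-risk group reaches 24, the expected high-risk count is at most 0.18. That is a recruitment failure, and a different t test does not repair it. The fallback of adding SNPs could change the sizes, with no assurance of equality.
- The direction of imbalance is not fixed, so a conservative test is also possible.
- Item a of the Study Design could be read literally as 12 high-risk against 24 low-risk participants. The same item asks for 24 children and 24 young adults, and Study Phases gives 24 per risk group, so this is probably a slip of wording.

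**Conclusion.** The point holds as a low-cost safeguard. There is no material error at the planned 24 v 24. If the achieved groups are unequal and their spread differs, Student's test and its interval could be wrong in either direction: roughly 6% to 8% at 18 v 24 and 9% to 11% at 12 v 24 when the smaller group is the more variable, and roughly 2% to 3% at 12 v 24 when the larger one is. These are scenarios resting on assumed splits, SD ratios of 1.5 to 2, normal data and a two-sided 5% level. That groups may end up unequal is well grounded in the plan's own procedures; how unequal, and with what difference in spread, cannot be read from it. The inability of Table 1 to fill both groups, and the two versions of the allele cut-offs, are separate matters that need their own resolution.

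**What to change.** In Study Design item c and in Aims 2 and 3, replace the unpaired Student's test with Welch's unequal-variance t test, reported with its confidence interval, for every high- versus low-risk comparison. Repeat the statement in section 6.3, which at present names no between-group t test. Make the change before data are seen, and do not make it conditional on a preliminary variance test.

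The cost is one line of wording, plus the small power loss shown above if groups are unequal but variances are equal. Add that if either group has only 2 or 3 participants, the comparison will be reported descriptively, since Welch's test is unreliable there. No calculation here supports extending the change to robust standard errors in the regression models, so that is not proposed.

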Specific Aim3: Determine the relationship between markers of DNL, liver fat accumulation and serum concentrations of lipids, uric acid and liver function markers before and after the fructose challenge

- We will measure serum concentrations of liver function markers, lipids and uric acid at week 0 and week 3;
- As in previous aims, data will be analyzed using students T test, and Pearsons correlations.

Subject Population	Inclusion Criteria
key criteria for Inclusion and Exclusion:	
 Subjects between 12 and 40 years No history of alcohol abuse (> 7 drinks per week) History of fructose intake of < 14 drinks per week Caucasian ethnicity BMI > 25kg/m² – 32kg/m² or 85th -99th percentile but otherwise healthy
	Exclusion Criteria
	
 ages < 12 and > 40 years Pregnant/lactating known alcohol abuse or fructose intake > 14 drinks per week not of Caucasian ethnicity glucose levels > 100 mg/dl if fasting, > 140mg/dl if within 2 hours post meal and > 200 mg/dl if random sample taking anti-hypertensive, anti-diabetic, uric acid and/or lipid-lowering medications known diagnosis of diabetes, fructose intolerance, chronic kidney disease, NAFLD or any liver-related disease, hypertriglyceridemia, polycystic ovary syndrome, hypothyroidism, obstructive sleep apnea, hypopituitarism and hypogandism BMI < 25kg/m² or > 32 kg/m² or < 85th or > 99th percentile Liver fat fraction >5% as per baseline MRI scan
Number Of Subjects	200 for first phase and 48 for the second and third phases
Study Duration	The first phase will be about 30 minutes and the second and third phase will be divided into two visits. Both visits in both phases will be about 3.5 hours each.
Study Phases	(1) Screening: We will screen participants for eligibility to participate in the study based on the inclusionary/exclusionary criteria specified above. The 200 children and young adults selected to participate will provide saliva which will be used to extract DNA and then genotype 10 SNPs. These SNPs are selected based on their association with de novo lipogenesis (DNL) or liver fat accumulation in previously published studies in Caucasians. We will select 12 children and 12 young adults with more than 15 risk alleles and 12 children and 12 young adults with less than six number of risk alleles.
Screening	
Study Treatment	
Follow-Up	

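### Aim 2 and part of Aim 3 are about de novo lipogenesis, but the plan names no marker of it

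*Combined protocol and SAP*

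**What the plan says.** **Aim 2 (synopsis).** The aim is to "Determine the impact of acute exposure of fructose on hepatic" *de novo* lipogenesis (DNL). The text then says "we will conduct oral fructose tolerance test at week 0 and week 3", and the one measurement listed is "We will measure liver fat using Fibroscan". The analysis is by "unpaired students T test and repeated measures ANOVA to differentiate the responses between and within the two groups, respectively", with no response variable given.

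**Aim 3 (synopsis).** The aim is to "Determine the relationship between markers of DNL, liver fat accumulation and serum concentrations of lipids", uric acid and liver function markers. The measurements listed are serum liver function markers, lipids and uric acid.

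**Measurements.** Section 4.2 (Biochemical phenotyping) names ALT, AST, GGT, uric acid, triglycerides, and total, HDL and LDL cholesterol. Section 5 mentions urinary biomarkers without naming any. Endpoint 6.1 is liver fat by MRI, Fibroscan and fatty liver index; 6.2 is serum liver function markers, lipids and uric acid. Section 6.3 plans a regression of an area under the curve (AUC) for the acute challenge and does not say of which analyte.

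**Meals.** The synopsis says "participants will be given standardized meals for the day prior to the baseline fructose challenge". Section 4.2 (Meals) describes one meal on the evening before part 1 of phase 2, a term that is not defined.

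**The concern.** DNL is in the study hypothesis and in the overall goal (section 2.1), which is to supply preliminary data for a larger application. If the plan is followed as written, the report on Aim 2 would either have no DNL result or present something else, such as a triglyceride curve or a Fibroscan reading, as if it were one. The Aim 3 correlations would lack one of their stated variables. A larger study designed around a genotype effect on DNL could then rest on data that do not bear on it.

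A smaller matter affects the same aim. The challenge is repeated at week 3, but the preceding diet is standardised only around baseline, so a difference between the week 0 and week 3 responses may partly reflect what was eaten the day before.

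**Working it through.** No figure in the plan can be reproduced here. The check is to set each DNL statement beside the measurements that could serve it.

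**1. Can Aim 2's listed measure show an acute effect?** The synopsis (Intervention, visit 2) and section 4.2 (Oral fructose challenge) both put Fibroscan before the drink. No post-drink scan is described. A change in Fibroscan from week 0 to week 3 would reflect three weeks of daily drinks, which is the prolonged exposure and not the acute one. Section 4.2 also describes Fibroscan as assessing stored fat and stiffness, not a rate of synthesis.

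**2. Is any named analyte a DNL marker?** Section 4.2 (Sample preparation) says the stored blood is for the biomarkers listed later in that section. Sorted by the classes that Aim 3 itself uses:

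| Class in Aim 3 | Named serum analytes | Count |
|---|---|---|
| Liver function | ALT, AST, GGT | 3 |
| Uric acid | uric acid | 1 |
| Lipids | triglycerides; total, HDL and LDL cholesterol | 4 |
| Markers of DNL | none | 0 |

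3 + 1 + 4 = 8, so all eight are accounted for and none is left for the DNL class. The three liver-fat measures (MRI, Fibroscan, fatty liver index) belong to Aim 3's liver-fat class.

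**3. Could triglycerides fill the role?** The Study Rationale says "High fructose intake has been shown to increase serum triglycerides, upregulate" DNL, reduce fatty acid oxidation and "decrease the clearance of very low density lipoprotein triglycerides in liver". These are separate effects. A rise in triglycerides after the drink could come from more synthesis or from slower clearance, and nothing else measured separates the two. Aim 3 also lists DNL markers apart from lipids.

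**4. What acute data exist?** Blood at 0, 1 and 3 hours, at weeks 0 and 3 (section 4.2, Sample preparation). The serum triglyceride and uric acid responses over three hours can therefore be analysed, although section 6.3 does not name them.

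**5. Meals.** If part 1 of phase 2 means the challenge, the synopsis and section 4.2 differ in whether the meals cover the day or only the evening. If it means visit 1, the section 4.2 meal precedes the MRI, which takes place the day before the challenge. On either reading, no standardised meal is described before the week 3 challenge. Section 7 has participants taking a study drink daily from the day after the first challenge. The day before the week 3 challenge therefore also differs from baseline in that respect unless the plan deals with it.

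**The case against.** **None named is not the same as none measured.** This stands. The urinary biomarkers are unspecified, endpoint 6.2 is an open list, and a figure is missing from the supplied text. A reader might infer that no DNL marker will be measured at all; the documents support only that none is named. A reader might also infer that a tracer measure was dropped, because references 11 and 12 (tracer-derived fat oxidation; rates of fat synthesis) are not cited in the text supplied. Missing text would explain that equally well.

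**The challenge follows a published test of lipogenic sensitivity.** It does, and section 6.3 cites the same source for the AUC. The protocol takes from it a challenge procedure and an AUC, but states no assay, and the source is not available here. The same citation is a reason not to go further on the AUC. A reader might infer that the AUC analysis is biased by fasting differences between the risk groups. The plan does not choose a form of AUC and gives no fasting values, so that is not supported.

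**The protocol uses lipogenesis and liver fat loosely.** This is partly right: the background (section 1) and the risk-allele definition in section 4.2 run them together. Some of the defect is therefore wording. But Aim 3 lists the two separately, so one cannot quietly stand for the other.

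**This is an exploratory pilot.** True, and section 6.4 concedes low power. That limits the severity, but the pilot's stated purpose includes DNL data.

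**Diet is partly controlled already.** Draws are fasting, participants are advised to avoid juices and sodas for the three weeks (section 1.3), and diet recalls are collected. These reduce the meal problem without removing it.

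**Conclusion.** The point holds in this form: no DNL marker is named anywhere in the documents (0 of 8 serum analytes, 0 of 3 liver-fat measures, urinary biomarkers unnamed), and the only measure listed under Aim 2 precedes the drink. As written, Aim 2 and the DNL part of Aim 3 cannot support a conclusion about DNL. This rests on the text alone, with no assumed figures.

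The reach is limited. MRI liver fat, objectives 2.2 and 2.3, endpoints 6.1 and 6.2 and the rest of Aim 3 are unaffected. An acute serum response can still be studied.

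The meal gap is real but secondary. It weakens the week 0 against week 3 comparison; it does not make Aim 2 unanswerable. The documents give no basis for putting a size on it.

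**What to change.** **Main change, one of two options.**

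- Restate Aim 2 as the acute serum triglyceride and uric acid response at 0, 1 and 3 hours. Remove Fibroscan as its acute outcome, put that response in place of the DNL markers in Aim 3, name these analytes as the AUC response in section 6.3, and draw no DNL conclusion.
- If the larger application needs DNL data, name the marker, assay, sampling times and analysis before any samples are run, and tie Aims 2 and 3 to it.

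**Secondary change.** Use the same standardised meal before the week 0 and week 3 challenges. Reconcile the synopsis with section 4.2 on what the meal is and which visit it precedes. State how the daily study drink is handled on the day before the week 3 challenge.

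**Cost.** The first option needs only wording, but it narrows the claim for Aim 2 and leaves the application without DNL data. The second adds an assay. The meal change means further standardised meals for up to 48 participants.
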